4 INTRODUCTION

This statistical analysis plan (SAP) describes the statistical methodology to be used for the reporting and statistical analysis of efficacy and safety clinical data as collected under SK Life Science clinical study protocol YKP3089C017 (amendment 2, 20 March 2015) during open-label extension (OLE) phase of the protocol.

All statistical methods in this SAP are in regulatory compliance with the specifications as detailed in the International Conference on Harmonization (ICH) Guidelines:

- E3: Structure and Content of Clinical Study Reports;
- E6: Guideline for Good Clinical Practice; and
- E9: Statistical Principles for Clinical Trials.

Table, listing and figure templates (TLFs) for the open-label extension of this phase 2b study are presented in a separate document.

All analyses described and TLFs programmed as mentioned in this SAP are to be included in sections 14 and 16 of the clinical study report (CSR). All computer outputs detailing the statistical computations are to appear in an appendix: Statistical Documentation in the CSR as specified in the ICH E3 Guidance.

The signatures on this statistical analysis plan indicate approval of the safety, statistical analyses as detailed in each section of this SAP. These sections are agreed upon by SK Life Science (the Sponsor) and QDS (the Vendor).

This SAP may be revised at the end of the clinical investigation and prior to database lock for open-label extension phase to reflect specific details regarding protocol deviations and/or other data analysis clarifications (if needed).

This SAP supersedes any statistical considerations which were identified in the study protocol. Substantial differences from the study protocol are identified in this plan. If additional analyses are required to supplement the planned analyses then they will be performed and identified in the appropriate section of the CSR.

Computer program validation methods are to be agreed upon by the Sponsor and Vendor. Quality Control (QC) of all statistical components including derived SAS analysis datasets and TLFs will be performed by the Vendor prior to delivery to the Sponsor. All computational methods will be checked for accuracy. All "SAS Notes" generated from the computers programs will be checked for appropriateness.

_

SK LS Protocol YKP3089C017

SAP-OLE Version Final_15May2021 Page 8 of 43

5 STUDY OBJECTIVES

The objectives of this study are:

- To determine the effective dose range of YKP3089 as adjunctive therapy for the treatment of partial seizures (primary objective).
- To evaluate the safety and tolerability of YKP3089 in the partial epilepsy population.

6 STUDY DESIGN AND VISIT SCHEDULE

This is a multicenter, double-blind, randomized, placebo-controlled study with an 8-week prospective baseline and an 18-week double-blind treatment period (including a 6-week titration phase and 12-week maintenance phase), followed by a 3-week blinded study drug taper period (for subjects leaving the study) or a blinded 2-week conversion period (for subjects participating in the open-label extension), with a final follow-up visit 2 weeks after the last dose of study drug.

Approximately 400 randomized subjects with partial-onset seizures will be screened at approximately 100 study sites worldwide to achieve the required sample size of 400 subjects. Study sites were classified by geographic region prior to randomization. The geographic regions defined in the study are as follows: Region 1= USA, UK, Germany, France and Australia; Region 2 = Korea and Spain; and Region 3: Remaining countries.

Subjects who have experienced at least 8 partial seizures including only simple partial seizure with motor component, complex partial seizures or secondarily generalized seizures during the baseline period without a seizure-free interval of greater than 25 days any time during those 8 weeks will be randomly assigned in a 1:1:1:1 ratio to receive placebo or YKP3089 100, 200, or 400 mg given once per day in the morning. Subjects must have at least 3 partial seizures during each of the two consecutive 4-week periods of the baseline.

Randomization was performed centrally, using an IWRS system. Randomization codes are based on a block randomization within study region.

Men and women 18 to 70 years of age, inclusive, in which subjects who meet inclusion/exclusion criteria (see study protocol) were permitted to enroll in this study.

Enrolled subjects are eligible to progress through the following study periods:

1. The Baseline/pre-treatment period consists of an 8-week prospective baseline period where pre-treatment seizure frequency information is collected. Subjects who have experienced at least 8 partial seizures during the baseline period without a seizure-free interval >25 days any time during the 8 week period may be randomized. Subjects must have at least 3 of these partial seizures during each of the two consecutive 4 week periods in

88

[figure not shown]
the baseline. A seizure diary check was performed by the CRO monitoring this protocol at Visit 3 (randomization) to confirm that these seizure frequency criteria were met during the 56 days prior to Visit 3.

2. The 18-week double-blind (DB) treatment period including:

- a. Subjects will first enter a 6-week titration phase, during which the initial dose will be 50mg/day. The planned increase in the daily dose will be 50mg/day/week increments until 200mg is reached and after which the dose will be increased by 100mg/day/week in subjects randomized to 400mg/day. During week 1, no dose reduction will be permitted. Subjects who had significant tolerability issues were to discontinue treatment with study drug. Subjects having tolerability issues for the first time during Weeks 2 to 6 will have their dose reduced by 50 or 100 mg depending on their attained dose at the time (Reduce by 50mg if taking 100mg, 150mg or 200mg; reduce by 100mg if on 300mg or 400mg). Subsequent to this reduction, subjects may at the discretion of the Investigator, recommence the upward titration by 50 mg increments towards their target dose until Week 6. If the subject cannot tolerate the new upward titration, the daily dose can be reduced one time by 50 mg through the end of week 8. Refer to Protocol Section 6.1.2.1 for details.
- b. Subjects will then enter a 12-week double-blind maintenance phase. The subjects were instructed to take their study medication once daily in the morning for 12 weeks. Those patients who withdraw prematurely will taper off the study drug.
- c. Subjects that did not participate in the optional open-label phase were to enter a 3 week, double blind taper period. The taper phase will last 3 weeks, followed by a final visit 14 days after the last dose of study drug. Refer to Protocol Section 6.1.2.3 for details on taper phase.
- 3. Only subjects who complete the double-blind maintenance phase will be given the option to continue treatment in an open-label extension phase. Refer to Protocol Section 6.1.4 for details. The open label extension includes:
 - a. The blinded 2-week crossover period (for subjects participating in the open-label extension), during which all subjects will be converted to a target dose of 300 mg once daily, of open-label YKP3089. During the first week of the conversion period, the investigator can increase or decrease the open-label dosage by 50-100 mg if clinically indicated. During the second week of the conversion period, the investigator can decrease the open-label dosage by 50-200 mg or increase the open label dosage by a maximum of 100 mg if clinically indicated.

- b. The open-label extension period: Refer to section 6.1.4.2 of the protocol for details on the open label extension.
- c. The taper period of 3 weeks with a final follow-up visit 2 weeks after the last dose of study drug. Refer to section 6.1.4.3 of the protocol for details and the table for taper period.

Figure 1 Study Flowchart

Study assessment chart for double-blind period is included in DB SAP. OLE SAP includes details for study assessment chart for OLE only.

Table 1 Study Assessment Flow Chart for Open-Label Extension Phase

Visit windows of ± 3 days allowed for Visits 9 and Visit 17 (end of study follow-up visit)				Treatme	nt		End of Study Follow-up		
Visit windows of ± 2 days allowed for Visits 11 and 12. Visit windows of ± 7 days allowed for all other open-label visits	Visit 9 First Day of	Visit 11	Visit 12	Visit 13	Visit 14		Visit 16 or Terminati on Visit	Post 1 year	Visit 17
Assessment	Day 127ª	Day 141	Day 155	Day 239	Day 323	Day 407	Day 491	Every 3 months ^b	14 days after the last dose
Inclusion/exclusion ^c	Х								
Vital signs ^d	Χ	Х	Х	Х	Х	Х	Х	Х	Х
Weight	Χ			X		Χ	Х	Xe	Х
Full physical examination	Χ						Х	X ^f	
Full neurologic examination	Х						Х		Х
Brief neurologic exam		X		X		Χ		Xe	
C-SSRS ^g	Χ	X	X	X	X	X	Х	Χ	Х
ECG ^h	Χ		X				X	X ^f	

Serum pregnancy test ⁱ									Х
Urine pregnancy test ⁱ	Х		Х		Х		Х	Xe	
Laboratory safety assessment ^j	Х		Х		Х		Х	Xe	Х
Urinalysis	Х				Х		Х	X ^f	Х
Concomitant medication	Х	Х	Х	Х	Х	Х	Х	Х	Х
Dispense/review/ collect seizure diary	Х	Х	Х	Х	Х	Х	Х	Х	
Drug accountability	Х	Х	Х	Х	Х	Х	Х	Х	Х
Dispense study drug	Χ	Х	Х	Х	Х	Х	Х	Х	
Adverse events	Х	Х	Х	Х	Х	Х	Х	Х	Х

C-SSRS = Columbia Suicide Severity Rating Scale; ECG = electrocardiogram; AED = antiepileptic drug.

- a. Visit 9 is the same as Visit 9 at the end of double-blind maintenance phase, except that study drug for 2-week blinded crossover period to open-label extension will be dispensed to subjects who will participate in the open-label extension.
- b. After 12 months of participation in the open-label extension phase, subjects will be re-evaluated. Those who are benefiting from treatment with YKP3089 may continue use of the drug at the discretion of the investigator, until development is stopped by SK Life Science Inc, or the product is approved for marketing, or anytime at the discretion of SK Life Science Inc.
- c. Subject should continue to meet the inclusion and exclusion criteria except for seizure frequency.
- d. Vital signs include blood pressure and heart rate (supine for 5 minutes followed by standing for 3 minutes). Respiration rate and oral temperature in the supine position.
- e. Every 6 months after Visit 16.
- f. Every 12 months after Visit 16.
- g. Administer the Since Last Visit version of the C-SSRS.
- h. 12-lead ECG. Additional ECGs should be performed at any other time if clinically indicated.
- i. If pregnancy is suspected at any time during the study, an interim test may be performed.
- j. Laboratory assessment: Safety assessment includes blood chemistry and hematology.

7 ASSESSMENTS

7.1 Baseline Data and Prior Medications

Demographic data (Date of Birth, Sex, Race and Ethnicity), characterizing patients at baseline will be collected on the Demographics eCRF.

Height and weight at baseline will be recorded on the Vital Signs eCRF.

The subject's date of past and present medical conditions, prior to study enrollment, will be recorded on a Medical History eCRF. Medical history data will include the Body System, verbatim text, start date, and end date or ongoing.

The subject's epilepsy/seizure history will be recorded on an Epilepsy/Seizure History eCRFs. Seizure identification and Etiology data will also be collected.

Physical Examination at screening will be recorded on the Physical Exam eCRF. These data will include Body System, a normal/abnormal indication, and a description of the abnormality.

All prescription and OTC medications taken by the subject during the 30 days before screening and up to the first dose of the study drug will be recorded on the Prior and Concomitant Medications eCRF. These data will include the verbatim medication name, indication for use, dose, route, frequency, start date, and end date or ongoing indication.

A full neurologic evaluation examination will also be made and recorded on the eCRF. If the subject has not had a recent CT or MRI, one will be performed and entered on the eCRF. An EEG may also be performed and entered on the eCRF.

Twelve-lead electrocardiograms (ECGs) will be collected at screening and will not be entered on an eCRF. Results will be returned electronically for inclusion in the clinical database.

Clinical laboratory evaluations will be will be collected at screening and results will be returned electronically for inclusion in the clinical database.

Serum or urine pregnancy test results, where applicable, will be entered into the eCRF.

The baseline version of the Columbia Suicide Rating Scale (C-SSRS) will be assessed at Visit 1 and entered on the eCRF.

7.2 Efficacy Assessments

Daily seizure information regarding the date, type and number of individual seizures will be entered into a seizure diary. These values are recorded on a

SK LS Protocol YKP3089C017

SAP-OLE Version Final_15May2021 Page 15 of 43 daily basis throughout the OLE phase, and are the basis for deriving all endpoints involving seizure frequency.

7.3 Safety and Tolerability Measures

Adverse event (AE) assessments will be recorded on the Adverse Events eCRF. The term AE is used to include both serious and non-serious AEs. Treatment emergent AEs (TEAEs) occurring during the study treatment period from the first dose of study drug medication up to and including 30 days after the end of treatment (i.e., not present at baseline or worsened in severity following start of treatment) should be reported as AEs and summarized. These data will include the verbatim term for the AE, start date, end date or indication of ongoing, severity, indication of Serious AE, SAE criterion, relationship to study drug, action taken, and outcome. AEs will be coded using MedDRA.

Concomitant medications will be recorded on the Prior and Concomitant eCRF and used to identify prohibited medications.

Vital signs will be recorded on the Vital Signs eCRF. These data will include pulse, supine blood pressure, orthostatic blood pressure, oral temperature, and respiration rate.

Physical examinations will be recorded on the Physical Exam eCRF. These data will include Body System, normal/abnormal indication, and a description of the abnormality.

Twelve-lead electrocardiograms (ECGs) will be collected and returned electronically and not entered on an eCRF.

A brief neurologic evaluation examination will be made and recorded on the eCRF.

Clinical laboratory evaluations will be collected and returned electronically and not entered on an eCRF. Clinical Laboratory Evaluations will include the following:

 Table 2
 Clinical laboratory Evaluations

Category	Evaluation items
Hematology	red blood cell (RBC) count, platelet count, hematocrit, hemoglobin, mean corpuscular hemoglobin, mean corpuscular hemoglobin concentration, mean corpuscular volume, red cell distribution width, reticulocyte count, white blood cell count and differential (basophils, eosinophils, lymphocytes, monocytes, and neutrophils) reported as absolute values
Chemistry	alkaline phosphatase, alanine aminotransferase, aspartate aminotransferase, bilirubin (total and direct), gamma-glutamyl transferase, blood urea nitrogen, creatinine, uric acid, sodium, potassium, chloride, carbon dioxide, albumin, calcium, glucose (fasting), and protein (total)
Urinalysis	pH, specific gravity, glucose, ketones, leukocyte esterase, nitrites, occult blood, protein, RBCs/hpf, white blood cells/hpf, bacteria, castes, epithelial cells, mucous threads, and crystals
Urine Pregnancy	β-НСС
Serology	Hepatitis B, Hepatitis C, and HIV antibody
Urine drug and alcohol	marijuana, opiates, cocaine metabolite, and amphetamines/methamphetamines, and alcohol

The follow-up version of the Columbia Suicide Rating Scale (C-SSRS) will be assessed at Visit 2 and all subsequent visits and entered on the eCRF.

7.4 Study Compliance

Information on subject drug compliance will be recorded on the study drug dispensing eCRF and the Study drug accountability eCRF. These data will include the dates and amount of drug dispensed and returned.

End of study data will be recorded on the End of Study eCRF. These data will include completion status, date of completion or discontinuation, primary reason for discontinuation, adverse event id (if discontinued due to AE), lost to follow-up information.

Protocol deviations may be identified in two ways: 1) through programmatic checks or 2) through medical reviews. The protocol deviations may include:

- 1) Known protocol violations identified from the subject qualification eCRF and/or inclusion/exclusion entry criteria;
- 2) Exclusionary medical history or entry laboratory results;
- 3) Prior or concomitant medication deviations;
- 4) ECG deviations; and
- 5) Study drug dosing deviations.

Details about predefined protocol deviations are included in Appendix 1.

8 STUDY PATIENTS

8.1 Analysis Population

Open-Label Extension Safety Evaluable Population (OLE-SE): All subjects treated in DB who continued into OLE phase and took at least one dose of open-label study medication. All OLE safety analysesdescribed in this SAP will be performed using OLE-SE.

Open-Label Extension Efficacy Analysis Population(OLE-EA): All subjects who entered in OLE phase, took at least one dose of open-label medication and have any seizure data recorded in OLE seizure diary. All OLE efficacy analyses descried in this SAP will be performed by OLE-EA

Double-Blind and Open-Label Extension Safety Evaluable Population: All subjects who received at least one dose of study medication in either DB period only (ie, subjects treated in DB who did not continue in OLE phase) or in both DB and OLE (ie, subjects included in OLE-SE population). This analysis population will be considered when reporting protocol deviations.

OLE analysis summary results will be presented by the following treatment groups:

- All YKP3089 OLE
- YKP3089 100mg DB to YKP3089 OLE
- YKP3089 200mg DB to YKP3089 OLE
- YKP3089 400mg DB to YKP3089 OLE

Placebo DB to YKP3089 OLE,

where YKP3089 100mg, 200mg, 400mg DB, and Placebo DB represent the randomized treatment group in double blind period and YKP3089 OLE represents the treatment given during OLE.

8.2 Subject Disposition

Subject disposition during OLE will be summarized using the number of subjects who opted for open-label extension as the denominator. Summary results will include, the number and percentage of subjects who completed the open-label extension, and the number and percentage of subjects who discontinued during the open-label extension along with the distribution of the reasons for discontinuation. Results will be summarized by OLE treatment groups.

For summary tables the reasons for termination/withdrawal recorded on the eCRF will be mapped as follows:

Reason for Termination/ Withdrawal on eCRF	Reason for Termination/ Withdrawal in Summary Table
Withdrew consent for reason other than adverse event	Withdrawal by Subject
Withdrew consent due to adverse event	Adverse Event
Terminated by PI for adverse event	Adverse Event
Terminated by Sponsor's medical monitor for adverse event	Adverse Event
Protocol violation	Protocol Violation
Lack of efficacy	Lack of efficacy
Pregnancy	Pregnancy
Lost to follow up	Lost to follow up
Death	Death
Other	Other

By-subject data listings will include reason for termination/withdrawal as recorded on eCRF.

SK LS Protocol YKP3089C017

SAP-OLE Version Final_15May2021 Page 19 of 43

8.3 Protocol Deviations

Protocol deviations will be reviewed by clinical team on ongoing basis. All protocol deviations during DB and OLE will be listed for all subjects included in Double-Blind and Open-Label Extension Safety Evaluable Population.

8.4 Demographic and Baseline Characteristics

All demographic measurements such as age, gender, height, weight, and BMI (computed using baseline weight and height) will be summarized by OLE treatment groups. All baseline safety measurements, such as ECGs, vital signs, and clinical laboratory values, will be summarized by OLE treatment groups for OLE safety evaluable population.

The continuous variables (e.g., age [years], height, weight, BMI), will be summarized using mean, standard deviation, median, minimum, and maximum values. Categorical (nominal) variables (e.g., gender, ethnicity, and race), will be summarized using number and percentage of subjects.

Baseline measurement for weight, height, BMI will be the last measurement before the first dose in the DB period. Baseline seizure frequency will be computed as defined in Section 9.

By-subject listings of all baseline characteristics will be produced.

8.5 Drug Exposure and Compliance

The extent of exposure to study drug as recorded on eCRF will be provided in a listing by-subject and by study week.

The following parameters will be derived:

- Exposure (days) = date of the last dose in OLE date of the first dose in OLE + 1
- Exposure (weeks) = (date of the last dose in OLE date of the first dose in OLE + 1)/7
- Exposure (months) = (date of the last dose in OLE date of the first dose in OLE + 1)/30.4
- Total subject years of exposure = sum of all subject total exposure days / 365.25.
- Modal daily dose defined as the dose taken the most days during OLE; in case of ties (i.e., 2 different dose levels taken the same number of days), modal dose will be defined as the highest dose between the two

Length of exposure (weeks and months) and modal dose will be summarized by OLE treatment groups using descriptive statistics.

The number and percentage of subjects for the following:

- exposure intervals: 0 to < 1 week,1 to < 2, 2 to < 4, 4 to < 12, 12 to < 24, 24 to < 48, 48 to < 96, 96 to < 144, 144 to < 192, 192 to < 240, 240 to < 288, 288 to <336, 336 to < 384, 384 to < 432, 432 to < 480, 480 to < 528, 528 to < 576, , >=576 weeks.
- exposure categories: >= 1 dose, >= 6, >= 12, >= 18, >= 24, >= 36, >= 48, >= 60, >= 72, >= 84, >= 96, >= 108, and >= 120 months.

Total subject years of exposure will be computed as sum of all subject total exposure days / 365.25 and reported in the summary table.

Drug accountability (tablets dispensed and tablets returned) will be listed by visit.

8.6 Prior and Concomitant Medications

Prior medications are defined as medications taken prior to the first dose of study drug medication and not ongoing at study visit 1 in DB.

Baseline antiepileptic drugs (AEDs) are AEDs that started prior to and are ongoing at the time of the first dose of study medication in double-blind period.

Concomitant AEDs/concomitant medications during OLE are identified as

- AEDs/medications with start date prior to the first dose date of study medication in OLE and end date on or after the first dose date of OLE study medication, OR
- AEDs/medications with start date prior to the first dose of study medication in OLE and ongoing at the end of OLE, OR
- AEDs/medications with a start date on or after the first dose of study medication in OLE.

Prior and concomitant AEDs/medications will be coded to a World Health Organization Drug Dictionary (WHO DD) Version 01Mar2013 term including ATC classification. A by-subject listing of prior AED, concomitant AED, and concomitant non-AED medications use will be produced.

The use of baseline and concomitant AED medications, prior medications, and concomitant non-AED medications will be summarized by OLE treatment group. The number and percentage of subjects taking each medication will be presented by ATC Classification.

In addition, the number of baseline AEDs per subject (mean, standard deviation, median, minimum, and maximum number of AED medications) will be included in the demographics and baseline characteristics summary table.

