As shown in [Table 2](#), the following will be performed at Visit 16 or at the time of early termination from the open-label phase.

At Visit 16, if clinically indicated, the subjects will begin the study drug taper described in Section 6.1.4.3. At the end of this drug taper, the subject will have discontinued YKP3089. The following assessments will be made at Visit 16:

- Record vital signs
- Measure weight
- Conduct full physical examination
- Conduct full neurologic examination
- Administer C-SSRS (Since Last Visit version)
- Perform 12-lead ECG
- Perform urine pregnancy test (for female subjects of childbearing potential)
- Draw blood for laboratory safety assessment
- Obtain urine for urinalysis
- Record concomitant medications
- Perform drug accountability
- Record AEs
- Review seizure diary

For subjects who completed 1 year of open-label treatment:

- Determine whether the subject is benefitting from open-label treatment with YKP3089

For subjects who are benefitting from open-label treatment:

- Dispense open-label medication

- Dispense seizure diary
- Schedule a return to occur in 3 months for next visit
- See section 9.3.9 for further instructions

For subjects leaving the open-label treatment due to any reasons at any time before 1 year or leaving at Visit 16 due to no benefit or any reasons:

- Dispense taper open-label study drug bottles as instructed by IWRS if needed
- Schedule a return to occur in 2 weeks of the last dose for Visit 17 if tapered
- Schedule a return to occur in 2 weeks for Visit 17 if not tapered

9.3.8 ***Visit 17, End of Study Follow-up (14 days from the last dose)***

Visit 17 represents the Follow-up Visit after discontinuation of study drug in the open-label extension phase. This final visit will take place 14 days after the subject's last dose of YKP3089—at any time during the open-label treatment or after 12 months of open-label treatment if there is no additional treatment beyond that point.

As shown in [Table 2](#), the following assessments will be performed at Visit 17:

- Record vital signs
- Measure weight
- Conduct full neurologic examination
- Administer C-SSRS (Since Last Visit version)
- Serum pregnancy test (for female subjects of child-bearing potential)
- Draw blood for laboratory safety assessment
- Obtain urine for urinalysis
- Record concomitant medications
- Perform drug accountability
- Record AEs

No study drug will be dispensed.

9.3.9 *Open-Label Extension Beyond Year One*

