10 SAFETY ENDPOINTS

10.1 Adverse Events

For open-label extension analyses, treatment-emergent AEs are defined as AEs with onset after the start of OLE study medication, up to last dose date of OLE study medication + 30 days, or onset before start of OLE study medication and worsened after starting OLE study medication, up to last dose date of OLE study medication + 30 days.

AE relationship to study drug can be classified by the investigator as definite, probable, possible, remote or unrelated. AEs severity can be rated as mild, moderate or severe.

SAEs will be captured from the time of study drug administration in OLE to 30 days after the last dose of study drug, and will be monitored until resolution or stabilization.

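### SAP 8.6 misfiles some medications: its prior rule joins two dates about eight weeks apart, and its extension concomitant rule has no end date (minor; descriptive tables only)

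*SAP*

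**What the plan says.** SAP 8.6 sets up three categories.

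- Prior: "Prior medications are defined as medications taken prior to the first dose of study drug medication and not ongoing at study visit 1 in DB".
- The baseline AED category: "AEDs that started prior to and are ongoing at the time of the first dose of study medication in double-blind period". This category exists for AEDs only.
- Concomitant during the OLE: a drug qualifies through any one of three limbs. The first two cover drugs begun before the first OLE dose and still in use on or after it. The third covers "AEDs/medications with a start date on or after the first dose of study medication in OLE" and stops there.

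The categories feed summary tables of the number and percentage of subjects on each medication, by ATC class and OLE treatment group.

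On collection, SAP 7.1 asks for "All prescription and OTC medications taken by the subject during the 30 days before screening and up to the first dose of the study drug", with start and end dates. During the extension, the Visit 17 procedures in Protocol 9.3.8 still include "Record concomitant medications", and that visit falls 14 days after the last dose.

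On the timing of Visit 1, Protocol Table 1 and 9.1.1 place it at Day -56, the start of the eight-week baseline. The SAP uses the label the same way; its section 7.1 says "The baseline version of the Columbia Suicide Rating Scale (C-SSRS) will be assessed at Visit 1 and entered on the eCRF".

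**The concern.** Each category should answer one question: was the drug finished before study drug began, or was it in use while study drug was being taken? The prior rule tests use against the first dose but tests continuation against a visit eight weeks earlier. Drugs whose status changes between those two dates can drop out altogether or be labelled finished when they were not. The OLE rule has a beginning and no end, while data collection runs past the last dose, so it also takes in drugs begun after treatment stopped.

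What is at stake is the accuracy of the prior and concomitant medication tables in the extension report. These are stated rules that give the wrong label when programmed literally; they are not simply short on detail.

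**Working it through.** No sample size, power or error rate is involved, so there is no planned figure to reproduce. The check applies the date rules literally to a set of medication histories.

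**Inputs.** Visit 1 = Day -56 (Protocol 9.1.1). First double-blind dose = Day 1 (SAP Appendix 2 convention). First OLE dose = Day 127 (Protocol Table 2). Last OLE dose = L, set at Day 491 for illustration; the result does not depend on it. Visit 17 = L + 14, with a window of ±3 days (Protocol Table 2), so L + 11 to L + 17.

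**Rules as written.** Prior: start before Day 1 and not in use at Day -56. Baseline AED: an AED, start before Day 1 and end on or after Day 1. OLE concomitant: (start before Day 127 and end on or after Day 127) or start on or after Day 127.

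**Bounded rules.** Prior: end before Day 1. Baseline AED: unchanged. OLE concomitant: start on or before L, and end on or after Day 127 or ongoing.

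| Medication history | SAP 8.6 as written | Bounded rules |
|---|---|---|
| Started and stopped before Visit 1 | prior | prior |
| Started before Visit 1, stopped in baseline | **no category** | prior |
| Started and stopped within baseline | prior | prior |
| Started in baseline, stopped in double-blind | **prior** (plus baseline AED if an AED) | baseline AED if an AED; otherwise none in this SAP |
| Started in baseline, ongoing in OLE | **prior** and concomitant (plus baseline AED if an AED) | concomitant (plus baseline AED if an AED) |
| Started before Visit 1, ongoing in OLE | concomitant (plus baseline AED if an AED) | same |
| Started and stopped in double-blind | none | none |
| Started and stopped in OLE, on drug (Days 200 to 300) | concomitant | concomitant |
| Started at L + 1, L + 10, L + 14 or L + 17 | **concomitant** (all four) | not concomitant (all four) |

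The table covers 12 histories. The bounded rules change 1 + 2 + 4 = 7 and leave 5 as they were. These are types of history, not frequencies, so 7 of 12 is not an error rate.

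**Does the heading of the OLE rule supply the missing end?** The rule is introduced as applying during the OLE. But SAP section 6 lists the follow-up visit two weeks after the last dose among the components of the extension, so that phrase does not confine the rule to time on drug.

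**How far does the open end reach?** Starts after the last dose enter the data mainly through Visit 17, so the excess is limited to roughly 14 days (at most 17 with the window). AEDs added during the YKP3089 taper are correctly concomitant, because drug is still being taken.

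**The case against.** The case against treating this as more than a wording matter is substantial, and much of it stands.

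- **Where to cut is partly convention.** Treatment-emergent adverse events in SAP 10.1 run "up to last dose date of OLE study medication + 30 days". That limit lies beyond L + 17, so applying it to medications would exclude essentially nothing recorded at Visit 17. The adverse-event rule therefore does not show where the medication rule should end. A bare cut at the last dose would also separate an event on day 5 after the last dose, which is treatment-emergent, from the drug given for it. This stands, and it is why later starts should be kept as a visible category.
- **Drug may still be present.** Protocol 4.4.2 gives mean half-lives of 50.2 to 60.4 hours for single doses of 100 to 300 mg. Taking five half-lives as a rough washout (an assumption), 5 × 50.2 / 24 = 10.5 days and 5 × 60.4 / 24 = 12.6 days. It would be too strong to say that every such drug had no overlap with YKP3089 in the body. It was still not taken during dosing, and the table does not separate the two.
- **Attribution of effect.** A reader might infer that the AED table would mislead on whether seizure reduction came from YKP3089 or from added AEDs. The documents do not support that. The table pools continuing and new AEDs and carries no timing, so it could not answer that question even when corrected. Start and end dates are collected, a by-subject listing of concomitant AEDs is planned, and OLE efficacy is descriptive.
- **Size.** A reader might also infer that a sizeable share of subjects is affected, chiefly those leaving for lack of efficacy or adverse events. The documents give neither the rate of leaving nor the rate of replacement AED use, so no percentage can be defended.
- **Prior rule.** Not every drug started or stopped in baseline is misfiled: one both started and stopped there is filed correctly. SAP 8.6 does not say that the categories are exclusive, so a drug started in baseline and carried into the OLE is at least also shown as concomitant. AEDs had to be stable for 4 weeks before Visit 1 and continued unchanged (Protocol 7.3, criterion 7), so few AEDs should be affected. If Visit 1 was meant as the first dosing visit, the rule would work, but neither document uses the label that way.

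**Conclusion.** Both defects hold on the text; the prior rule is the clearer one. As written, it loses a drug ongoing at Visit 1 and stopped before the first double-blind dose, and it calls prior a drug begun in baseline that continues on treatment. The OLE concomitant rule counts drugs begun after the last OLE dose, and recorded by Visit 17, with those taken during treatment.

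The impact is minor. It is confined to descriptive medication tables, falls mostly on non-AEDs for the prior rule, and is limited to about two weeks of follow-up for the concomitant rule. No efficacy endpoint, hypothesis test or adverse-event derivation depends on these flags. The conclusion assumes that Visit 1 means the Day -56 screening visit and that the rules are programmed literally. Double-blind medication reporting falls under a separate SAP that is not available here, so nothing is claimed about it.

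**What to change.** In SAP 8.6:

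1. Define prior medications as those stopped before the first double-blind dose, and drop the reference to Visit 1.
2. Replace the three OLE limbs with one rule: start date on or before the last OLE dose date, and either end date on or after the first OLE dose date or ongoing.
3. Report drugs started after the last OLE dose as a separate post-treatment category, so that treatments for adverse events in the 30-day window stay visible.

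A non-AED started in baseline and stopped during the double-blind period then has no category in this SAP; a sentence should say that the double-blind report covers it. The cost is a few sentences and a revised derivation flag, with no new data, since start and end dates are already collected. SAP section 4 allows revision before the OLE database lock.
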